### 2.4 Exclusion Criteria

Women with the following conditions will not be eligible for this study:

- Acute infection, or apparent inflammatory process

Principal Investigator (Last, first, middle): [name]

- Severe anemia (Hb of < 8g/dL)
- Severe malnutrition (body mass index <14)
- Presence of occult blood in stool as detected by HemoQuant test ( Schwartz et al 1983).
- History of chronic blood loss e.g. polymenorrhoea
- Presence of *Ancylostoma duodenale* (hook worm) in stool
- Pregnant and lactating women ( initial 2 months of lactation )

## 2.5 Laboratory Methods

Hb will be analyzed using the cyanomethemoglobin method (Sigma kit, Sigma, St. Louis, MO). Transferrin saturation will be assessed by analysis of Fe and total Fe-binding capacity (TIBC) (Sigma kit), and plasma ferritin and circulating transferrin receptor will be measured by ELISA (Ramco, Houston, TX). Commercial quality control materials (DiaMed, Cressier sur morat, Switzerland, Sigma and Ramco) will be analyzed together with all series of samples analyzed for Hb, Fe, TIBC and plasma ferritin.

### 2.6.1 Outcome Measures

- Prevalence of Hp infection and hypochlorhydria before and after intervention
- Prevalence of IDA in each group before and after the intervention
- Rise of serum Hb and SF, transferrin saturation, and reduction in sTfR before and after intervention
- Change of gastric acid output before and after intervention.

## Facilities Available

---

Describe the availability of physical facilities at the place where the study will be carried out. For clinical and laboratory-based studies, indicate the provision of hospital and other types of patient's care facilities and adequate laboratory support. Point out the laboratory facilities and major equipment that will be required for the study. For field studies, describe the field area including its size, population, and means of communications. (TYPE WITHIN THE PROVIDED SPACE).

---

The study will be carried out under the Clinical Science Division of ICDDR,B. The study population will be recruited from Nandipara, a peri-urban community, situated 7 miles northeast of Dhaka city Centre. The community has a population of 4,500 with about 750 reproductive age women, in an area of approximately 3 square miles. The prevalence of Hp infection in women of this community is about 80%. Since 1985, ICDDR,B operates a weekly clinic for provision of care to the population for their minor illnesses.

Blood analysis including Hb, SF and sTfR, and measurement of gastric acid concentration will be performed in the laboratories of the Laboratory Sciences Division of ICDDR, B. Breath samples for UBT will be sent to the University of Basel, Switzerland where C will be measured by mass spectrometry (IRMS).

Principal Investigator (Last, first, middle): [name]

## Data Analysis

Describe plans for data analysis. Indicate whether data will be analyzed by the investigators themselves or by other professionals. Specify what statistical software packages will be used and if the study is blinded, when the code will be opened. For clinical trials, indicate if interim data analysis will be required to monitor further progress of the study. **(TYPE WITHIN THE PROVIDED SPACE).**

Principal Investigator (Last, first, middle): [name]

Data will be entered onto personal computer (PC) and analyzed by the investigators themselves using the Windows version of the Statistical Package for Social Science (SPSS).

Chi square test will be used for comparison of the proportions of IDA in Hp-infected women with normal acid secretion (>300 AUC) versus women with low acid secretion (AUC <300).

Clinical characteristic such as age and weight, and laboratory characteristics such as Hb, SF, and sTfR concentration will be compared among the groups by one way analysis of variance (ANOVA). When significant F ratio ( $p < 0.05$ ) is obtained, means will be compared by student's t-test using multiple comparison procedure. Outcome variables e.g. change in the Hb, SF and sTfR, and gastric acid output before and after intervention in each group will be compared using paired t-test. Data with skewed distribution will be normalized using log transformation, and the t-test will be applied on transformed data. Chi-square ( $X^2$ ) test will be applied for comparison of binary variables e.g. the incidence of Hp infection with hypochlorhydria and IDA before and after therapy, and also for comparison between groups. The Odd's Ratio (OR) and Confidence Interval (CI) will be calculated. Multivariate analysis (logistic regression and multiple regression) will be done for adjustment of confounding variables such as age, socioeconomic status, and nutritional status .

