*Helicobacter pylori* (Hp) is a major gastrointestinal pathogen that causes gastritis and low gastric acid production. Gastric acid is one of the most important luminal factors necessary for optimal non-haeme iron (Fe) absorption. Thus, low gastric acid is a risk factor for iron deficiency anemia (IDA), which affects millions of people, primarily infants and women in the reproductive age. We hypothesize that poor bioavailability of iron in these countries might be related to low gastric acid output resulting from Hp infection. The frequency of low gastric acid secretor and IDA in such population is not known. We, therefore, propose to investigate the frequency of *H. pylori*-associated low gastric acid secretor (hypochlorhydria) and to evaluate its role in causing IDA in women. One hundred sixty women in the reproductive age, living in Nandipara, a peri-urban community of Dhaka city will be studied to ascertain the frequency of *H. pylori*-associated low acid output and IDA. To investigate the role of Hp in causing hypochlorhydria and IDA, an intervention study is also planned. Four groups (25 in each group) of Hp-infected women with IDA and hypochlorhydria, and another group (fifth group) of 25 women with normochlorhydria will be studied. Hp infected women with IDA and hypochlorhydria will be assigned to one of the four interventions: (i) anti-Hp therapy (triple-therapy with clarithromycin, amoxicillin and omeprazole), (ii) anti-Hp triple therapy plus iron (ferrous fumarate), (iii) iron therapy alone, or (iv) placebo. The fifth group of women with Hp infection and IDA but without hypochlorhydria will be treated with anti-Hp therapy.

Urea breath test will be used for identification of *H. pylori* infection. Iron status will be determined by analyzing hemoglobin, serum ferritin, and circulating transferrin receptor. Electrical Impedance Tomography (EIT) will be used to assess basal and pentagastrin-stimulated gastric acid outputs. Urea breath test, iron status, and EIT will be repeated at the end of intervention, and at 3 and 6 months from the time of initiation of intervention therapy.

This study is expected to provide useful, new information on the role of *H. pylori* infection and hypochlorhydria in the etiology of IDA. The findings of this study, therefore, are likely to influence the design of iron fortification strategies/programmes for reducing the burden and consequences of IDA in the developing countries.

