## DESCRIPTION OF THE RESEARCH PROJECT

### Hypothesis to be tested:

Concisely list in order, in the space provided, the hypothesis to be tested and the Specific Aim of the proposed study. Provide the scientific basis of the hypothesis, critically examining the observations leading to the formulation of the hypothesis.

Iron deficiency anaemia (IDA) is the single largest nutritional deficiency globally, and is a major health problem in the developing countries. *Helicobacter pylori* (Hp) infections are also very common in the developing countries. This important gastrointestinal pathogen causes chronic gastritis, which ultimately progress to gastric atrophy and may thus impair absorption of iron. We, therefore, hypothesize that in Bangladeshi women in the reproductive age:

1. chronic *Helicobacter pylori* infection is a major cause of low gastric acid output (hypochlorhydria), which in turn
2. significantly contributes to the development of iron deficiency anaemia in this population.

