### 2.a Gastrointestinal function and iron deficiency anaemia

The relationship between IDA and gastrointestinal functions including gastric acid secretion has been studied in children and adults. Nieman and his colleagues studied 14 iron-deficient infants and children, and observed profound suppression of gastric acid secretion in majority of the subjects (Niemann et al 1964). Studies in India have observed reduced gastric acid secretion in children (Ghosh et al 1972) and in adults (Sherman et al 1966) with iron deficiency anaemia. Reduction of acid secretion including histamine-fast achlorhydria also been reported in other Indian studies (Desai et al 1967, Desai et al 1968); compared to controls, acid outputs were significantly reduced in patients with iron deficiency. Histological abnormalities of the gastric mucosa suggestive of chronic gastritis were demonstrated in 61% of the patients in these studies. Other studies have observed very high incidence (75%) of chronic gastritis with iron deficiency anaemia (Ikkala & Siuarala 1964). However, it is not known if these abnormalities precede iron deficiency anemia. An early acquisition of infection in children in developing countries suggests that Hp-related chronic gastritis might precede iron deficiency anaemia in these countries.

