## 2. Part 2: Testing of the second objective

### Randomized, double-blind, placebo-controlled, community trial

#### 2.1 Methods

To determine if there is a causal relationship of IDA with Hp infection, or if Hp infection has any relationship with IDA, an intervention study will be conducted on 100 Hp-infected women with hypochlorhydria and IDA. They will be randomized in equal numbers to receive either of the following four interventions:

- (i) Anti Hp therapy: A combination of 500mg clarithromycin twice daily + 500mg amoxicillin twice daily + 40 mg omeprazole once daily for 14 days
- (ii) Anti Hp therapy plus iron: The above + ferrous fumarate containing 60-mg elemental iron each day for 60 days
- (iii) Iron alone: Ferrous fumarate containing 60-mg elemental iron each day for 60 days
- (iv) Placebo: Starch powder

**Fifth group:** There will be a fifth group of 25 women with Hp infection but without hypochlorhydria. This group is required to observe the influence of hypochlorhydria *per se* on IDA. This group will also be treated with Anti-Hp therapy plus iron.

The therapies will be provided in gelatin capsules and will be fed daily in morning and at the evening. The women in the placebo group will receive same amount of starch powder in identical capsules for 60 days. To keep the study blind, all therapies will be kept in identical container and will be fed by a health worker who will remain unaware of the nature of the study and the contents inside the bottles.

The women will be followed for six months after the end of intervention. Hb, SF, and sTfR will be determined at the end of intervention and also, 3 and 6 months after the intervention. Urea breath test will also be performed at the same time. EIT will be repeated 6 months after intervention. The women in the placebo groups will be given anti-Hp therapy plus iron as indicated above at the end of study period of 6 months. Similarly the group (iii) women will also provided anti-Hp therapy at the end of the study. The dose of iron conforms to that used in Bangladesh ( Kolsteren et al 1999).

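### The only analysis named for continuous gastric acid output is a within-group paired t-test, which cannot attribute a rise in acid to iron or to anti-Hp therapy although both are randomised

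*Protocol*

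**What the plan says.** All references are to the H. pylori proposal in the Protocol.

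- **Hypothesis.** The second hypothesis is directional: low acid output "significantly contributes to the development of iron deficiency anaemia in this population" (Hypothesis to be tested).
- **Background.** Section 2.a cites studies of reduced acid and gastritis in iron-deficient patients, then says: "However, it is not known if these abnormalities precede iron deficiency anemia". It goes on to argue for one order: "An early acquisition of infection in children in developing countries suggests that Hp-related chronic gastritis might precede iron deficiency anaemia".
- **Design.** Section 2.1 randomises 100 infected women with hypochlorhydria and IDA equally to anti-Hp therapy, anti-Hp plus iron, iron alone or placebo. Section 1.1.2 defines hypochlorhydria as an EIT AUC below 300. A non-randomised fifth group of 25 women without hypochlorhydria is added: "This group is required to observe the influence of hypochlorhydria" on IDA.
- **Acid as an outcome.** Section 2.6.1 lists change in gastric acid output. Section 2.1 says "EIT will be repeated 6 months after intervention". The Project Summary instead has EIT at the end of intervention and at 3 and 6 months from the start of therapy.
- **Analysis.** Data Analysis gives the cross-sectional test ("Chi square test will be used for comparison of the proportions of IDA in Hp-infected women with normal acid secretion", against women with AUC below 300). Change in Hb, SF, sTfR and acid output gets a paired t-test within each group. Binary variables get chi-square tests before against after and between groups. It also says "Multivariate analysis (logistic regression and multiple regression) will be done for adjustment of confounding variables".

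**The concern.** Part 2 holds a randomised answer to two questions about acid: does anti-Hp therapy restore it, and does iron restore it? The second matters because the background leaves open whether iron deficiency itself lowers acid. The stated test for continuous acid output uses neither randomised contrast. It asks only whether each arm moved from its own starting point, in women enrolled because that starting point was low.

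The comparisons of low-acid with normal-acid women cannot fill the gap. The chi-square and the fifth group both compare women by an acid status that was observed, not assigned. The association would be positive whether low acid leads to IDA or IDA leads to low acid.

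The stake is the causal chain from infection through low acid to anaemia, and the fortification message drawn from it in section 4 (Study objectives). A significant within-arm rise could be reported as recovery due to treatment when it is not. A recovery of acid due to iron could go unexamined.

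**Working it through.** **1. The plan's own sample size.** Section 2.3 uses 95% against 60% correction of anaemia, two-sided 5% and 80% power:

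n = 2 × 0.775 × 0.225 × (1.96 + 0.86)² / 0.35² = 22.64, so 23 per group.

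With z = 0.8416 for 80% power the result is 22.35, again 23. The stated figure reproduces. Allowing 10% dropout, 23 / 0.9 = 25.6, against 25 enrolled, which is close enough. This size was set for anaemia correction, not for acid. The protocol gives no SD, effect size or reliability for EIT AUC, so everything below on acid rests on assumed ranges.

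**2. What the paired test does when nothing changes.** Setup: AUC approximately normal; women enrolled if the screening value is in the lowest 60% (section 1.1.5 assumes 60% of infected women are hypochlorhydric); the screening EIT serves as baseline, since no separate baseline EIT is described; no true change; 23 women per arm; 1,500 simulated trials per row (simulation error up to about 2 points).

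| Assumed test-retest reliability | Paired t-test in one arm rejects | Between-arm t-test rejects |
|---|---|---|
| 0.95 | 8% | 5% |
| 0.90 | 10% | 6% |
| 0.80 | 15% | 5% |
| 0.70 | 22% | 4% |

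The excess in the middle column is regression to the mean. It acts equally on all four randomised arms, so it cancels in a between-arm comparison.

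**3. Whether the between-arm contrast is feasible.** Noncentral t, two-sided 5%, noncentrality d × √(n/2):

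- Iron alone against placebo, 23 v 23, d = 0.8: 0.8 × √11.5 = 2.71, power 75.6%.
- Iron (arms ii and iii) against no iron (arms i and iv), 46 v 46, d = 0.8: 0.8 × √23 = 3.84, power 96.7%.
- The same contrast, d = 0.6: 0.6 × √23 = 2.88, power 81.2%.

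By the normal approximation, the difference detectable with 80% power is 2.80 × √(2/23) = 0.83 SD for two single arms and 2.80 × √(2/46) = 0.58 SD when pooled. Pooling assumes the iron effect is the same with and without anti-Hp therapy.

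**4. What the cross-sectional chi-square can show.** On the protocol's prevalences, 160 × 0.8 = 128 infected women, of whom 128 × 0.6 ≈ 77 have low acid and 51 normal acid. With 70% IDA in the low-acid group, power is 63%, 81% or 93% if IDA in the normal-acid group is assumed to be 50%, 45% or 40%. The test can find an association. No sample size lets it show direction.

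**5. The fifth group.** Against arm (ii), with 23 each, power is 33% for 95% v 80% corrected and 61% for 95% v 70% (the lower rates are assumed). The comparator is itself unclear. The Project Summary says "The fifth group of women with Hp infection and IDA but without hypochlorhydria will be treated with anti-Hp therapy", while section 2.1 gives that group anti-Hp therapy plus iron and does not state that its members have IDA.

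**The case against.** The strongest reply is that the protocol does more than the paired test. The fifth group is a prospective element aimed at the role of low acid, and regression adjustment is planned. Chi-square tests between groups are planned for binary variables, with an example that includes hypochlorhydria. The ANOVA list is open-ended, and a named secondary contrast could be left to an analysis plan. Section 2.a also argues that gastritis may come first, and Part 1 is presented as a prevalence study.

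Much of this stands, and it rules out several stronger readings that a reader might infer:

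- *That the chi-square is the only test of low acid against IDA.* The fifth group and the regressions also bear on it. Neither is randomised by acid status, however, and the listed covariates (age, socioeconomic and nutritional status) do not settle direction.
- *That the protocol concedes low acid follows iron deficiency.* It says the order is unknown and then leans towards gastritis first.
- *That no between-arm comparison touches acid at all.* The binary example mentions hypochlorhydria, but combined with infection and IDA. Read as a composite, it changes when iron corrects IDA even if acid does not move.
- *That the cross-sectional association supports the second hypothesis only if iron fails to restore acid.* Non-significance in a trial of this size is not evidence of no effect, and both directions can hold at once.

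The reply does not rescue the paired t-test. That is an analysis the protocol states, not a detail it leaves open. It is also fair to say that the false-positive rates depend on assumed reliabilities, that iron alone is expected to correct anaemia in only 60%, and that a null result at a late EIT could reflect waning after iron has stopped.

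**Conclusion.** Wrong as written: a within-group test is the only analysis stated for a continuous outcome measured in randomised arms whose members were all selected for low values of it. It cannot attribute a rise in acid to iron or to anti-Hp therapy. Under no true change it would report a change in about 8% to 22% of trials per arm, against about 5% for a between-arm test. These figures assume reliability of 0.95 to 0.7, approximate normality, selection of the lowest 60%, and the screening EIT as baseline. A separate baseline EIT after screening would shrink the excess, but the paired test would still not identify the cause of a change.

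The non-randomised comparisons of low with normal acid remain useful as association. They cannot establish that low acid precedes IDA. The between-arm contrast would not settle direction completely either, but it is a randomised estimate of whether iron affects acid, which the stated analysis lacks. Its power is adequate only for moderate to large effects: about 81% for an assumed 0.6 SD when pooled, with no interaction.

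**What to change.** In Data Analysis:

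1. Replace the within-group paired t-test for acid output with a comparison of follow-up EIT AUC across the four randomised arms, adjusted for baseline AUC.
2. Within it, name a secondary contrast of iron against no iron, stratified by anti-Hp therapy, reported with its confidence interval. State that pooling assumes no iron-by-anti-Hp interaction, and show the estimates within each anti-Hp stratum.
3. Describe the chi-square of IDA by acid status as showing association only. Make its interpretation independent of whether the iron contrast is significant.
4. Reconcile the EIT schedule between the Project Summary and section 2.1, and fix which EIT is the follow-up value for this analysis. Reconcile the two descriptions of the fifth group as well, since they determine which randomised arm it can be set beside.

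The cost is a little more analysis work and some wording. No extra patients are needed, and both schedules already include a follow-up EIT.

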#### 4. Study objectives

Once acquired, Hp infection remains throughout the life, causing chronic gastritis, a risk factor for development of gastric atrophy and gastric cancer (Kuipers et al 1995). Gastric acid is the most important luminal factor necessary for optimal absorption of non-heme iron Fe (Skikne et al 1981). It is possible that Hp infection may reduce absorption of Fe consequent to gastric atrophy and achlorhydria, or due to a transient hypochlorhydria during active infections. Either of these mechanisms would result in an increased susceptibility of IDA. Hp-infected individuals have been found to have reduced levels of serum ferritin (Milman et al. 1998).

There is no published information on the relationship between Hp infection and gastric acid secretion. We plan to obtain information on the prevalence of reduced gastric acid secretion among Hp-infected subjects, and also hope to evaluate if Hp infection *per se* is a factor in causing IDA.

If, as hypothesized, Hp-linked hypochlorhydria is found to be a factor for IDA, it will help address an important issue with regards to effectiveness of Fe-fortification program since ferrous fumarate, that requires gastric acid for its bioavailability, is the used as Fe-fortificant in the developing countries.

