#### 2.2 Randomization

An experienced person not related in any way with the study will prepare a master randomization chart. A permuted block randomization with variable block length will be used. Box containing anti-Hp therapy, iron therapy, or placebo will be identical in appearance and will be arranged in sequence that corresponds to the randomization chart which will be sequentially numbered. The serial number of the box will correspond to the random number of women enrolled in the study. As one group of women would receive anti-Hp therapy and Fe therapy

Principal Investigator (Last, first, middle): [name]

simultaneously, there will be two boxes (boxes A and B) for each group of women to make the study double-blind. For women belonging to anti-Hp plus iron therapy, one box will contain anti-Hp therapy and the other box will contain Fe therapy. For women in the iron therapy or anti-Hp therapy groups alone, one of the boxes will contain active drug and the other will contain placebo for the other therapy. As the duration of therapy of anti-Hp therapy is 14 days, the women belonging to this group will be provided placebo capsules for the rest 44 days to maintain the double-blind nature of the study.

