### 2.3 Sample size

The sample size is determined with the assumptions that anaemia will be corrected in 95% women with Anti-Hp therapy plus iron-therapy, while iron therapy alone will correct anaemia in 60% of the women. Thus, the worthwhile difference (D) in correction of anemia will be:

$$D = 95 - 60 = 35\%$$

At 5% level of significance (type I error of 5%) with 80% power (type II error of 20%), and to detect a 35% difference in the outcome (correction of anaemia), the sample size has been estimated as follows:

$$n = 2 P(1-P) * (Z_{\alpha/2} + Z_{\beta})^2 / D^2$$

Where:  $P = (P_1 + P_2) / 2 = (95 + 60) / 2 = 77.5 \%$   
(  $P_1$  is 95% and  $P_2$  is 60% )

$$\begin{aligned} n &= 2 * 0.775 (1-0.775) * (1.96 + 0.86)^2 / (0.35)^2 \\ &= 1.55 * 0.225 * (2.82)^2 / 0.1225 \\ &= 0.34875 * 7.95 / 0.1225 \\ &= 22.6 \\ &\cong 23 \text{ subjects in each of the five groups} \end{aligned}$$

Based on previous study in the same community, we anticipate a drop out rate of approximately 10%. Therefore, the number of women to be enrolled is 25 in each group i.e.  $25 * 5 = 125$  women in total in 5 groups.

The reported prevalence of Hp infection is 80%. We estimate 60 % of infected population will be hypochlorhydric. of whom 70% will have IDA. We need to screen 298 ( $100 / 0.8 * 0.6 * 0.7$ ) women to identify 100 infected women (for four groups) with hypochlorhydria and iron deficiency anemia. As 160 women will be enrolled under the first part of the study we will require 138 ( $298 - 160 = 138$ ) additional women to be screened under the second part of the study.

We need a fifth group of 25 women with Hp infection but without hypochlorhydria. They will be selected from among these 260 women.

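### The four randomised H. pylori arms are a 2x2 of anti-Hp by iron, but no stated analysis combines the two anti-Hp contrasts or estimates the interaction, and changes are tested only within arms

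*Protocol*

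**What the plan says.** The file holds two protocols; this point concerns only the second, on H. pylori, hypochlorhydria and iron deficiency anaemia (IDA).

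- **Design (2.1 Methods).** The section states that "an intervention study will be conducted on 100 Hp-infected women with hypochlorhydria and IDA", and that "They will be randomized in equal numbers to receive either of the following four interventions": (i) anti-Hp therapy, (ii) anti-Hp plus iron, (iii) iron alone, (iv) placebo. Arm (ii) is defined as "The above + ferrous fumarate containing 60-mg elemental iron each day for 60 days".
- **Blinding (2.2 Randomization).** Each woman has two boxes. In the single-therapy arms "one of the boxes will contain active drug and the other will contain placebo for the other therapy".
- **Fifth group (2.1 Methods).** "There will be a fifth group of 25 women with Hp infection but without hypochlorhydria". It is not one of the four randomised arms.
- **Purpose.** Specific Aims asks whether H. pylori is causally linked to IDA, and 4. Study objectives says the investigators "hope to evaluate if Hp infection *per se* is a factor in causing IDA".
- **Sizing (2.3 Sample size).** One contrast is sized: (ii) at 95% corrected against (iii) at 60%.
- **Analysis (Data Analysis).** Age, weight, Hb, ferritin and transferrin receptor "will be compared among the groups by one way analysis of variance (ANOVA"), then by t-tests with a multiple comparison procedure if F is significant. Changes in Hb, ferritin, transferrin receptor and acid output are tested within each group by paired t-test. Binary outcomes get chi-square tests before v after and between groups, with odds ratios and confidence intervals. Logistic and multiple regression are described for adjustment of confounders.

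**The concern.** The four arms are the cells of a crossed design, and the double dummy supplies what a crossed design needs. The stated methods treat them as unrelated groups. Two things are lost.

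First, randomisation gives two independent estimates of the anti-Hp effect: (ii) v (iii) with iron, and (i) v (iv) without. Nothing combines them, although together they answer the causal aim with all 100 women.

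Second, 3.1 Fe fortification and 4. Study objectives argue that ferrous fumarate needs gastric acid to be absorbed. That predicts a larger anti-Hp effect with iron than without. The matching quantity, the anti-Hp-by-iron interaction, is not among the stated analyses.

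The paired t-tests add to the problem. A significant change in one arm and a non-significant one in another is not a comparison of the arms. For the continuous outcomes named as changes, the protocol therefore states no randomised comparison unless the ANOVA sentence is read to cover them.

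**Working it through.** **Inputs.** From 2.1 and 2.3: 25 enrolled and 23 analysed per arm, two-sided 5%, 95% corrected in (ii), 60% in (iii). Not in the documents, so assumed: correction rates in (i) and (iv), and effect sizes in SD units.

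**The plan's own figure.** n = 2P(1−P)(z₁+z₂)²/D² with P = 0.775 and D = 0.35 gives 0.34875 × 7.95 / 0.1225 = 22.6, so 23. With 0.842 in place of the protocol's 0.86 it is 22.3, again 23. Power of 23 v 23 at 95% v 60% is 83% (normal approximation, pooled variance) to 88% (unpooled variance, or simulated uncorrected chi-square). The sizing stands.

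**Standard errors, n per arm, common SD σ.**
- One pairwise contrast: σ√(2/n).
- Average of the two anti-Hp contrasts: σ√(1/n), smaller by a factor of 1.41.
- Interaction (difference of the two contrasts): σ√(4/n), twice that of the average.

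Detectable difference at 80% power, n = 23, multiplier 1.96 + 0.842 = 2.80:
- pairwise 2.80 × √(2/23) = 0.83 SD
- average 2.80 × √(1/23) = 0.58 SD
- interaction 2.80 × √(4/23) = 1.17 SD

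**Continuous outcome, equal effect with and without iron (noncentral t).**

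| True effect | 23 v 23 | 46 v 46 |
|---|---|---|
| 0.5 SD | 38% | 66% |
| 0.6 SD | 51% | 81% |

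The pairwise figures are unadjusted; a multiple comparison procedure would lower them.

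**Break-even, continuous outcome with equal variances.** Let the effect without iron be r times the effect with iron. The average is the stronger test when (1 + r)/2 exceeds 1/√2, that is r > √2 − 1 = 0.41.

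**Binary outcome at the protocol's 95% v 60%.** Simulated Mantel-Haenszel test stratified by iron, 23 per arm; (ii) v (iii) alone has 88% throughout.

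| Assumed (i) v (iv) | Stratified test |
|---|---|
| 30% v 10% | 93% |
| 20% v 10% | 83% |
| 15% v 10% | 75% |
| 5% v 5% | 75% |
| 10% v 10% | 66% |
| 20% v 20% | 54% |
| 30% v 30% | 48% |

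**Interaction, risk-difference scale, normal approximation, placebo rate 5% to 30%.** Power is 51–78% if anti-Hp adds nothing without iron, and 13–17% if it adds 20 points.

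**The case against.** Sizing and testing (ii) v (iii) is a legitimate multi-arm choice, and it is adequately powered on the protocol's inputs. If anti-Hp works mainly by improving iron absorption, as the protocol argues, that contrast is also the stronger test. This stands, and it is why the contrast must stay the main comparison.

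A reader might infer that the plan throws away half its women and that pooling brings a large rise in power. The documents do not support that. The 51% to 81% gain needs equal effects with and without iron, which sits badly with the protocol's mechanism. A binary gain of about 25 points (49% to 74%, at 30% v 10% without iron) appears only if 85% is put in place of the protocol's 95%. At 95% v 60% the gain is about 5 points at best among the cases shown, and a loss in the rest.

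The ANOVA sentence may partly describe comparability of the groups, since it names age and weight beside the laboratory values. That is fair. On that reading, however, the named changes are left with paired t-tests only, and a between-arm model is needed more.

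The regression models list confounders only as examples and do not specify treatment terms, and a statistical analysis plan, not shown here, could add both factors. So one cannot say the interaction will never be estimated, only that no stated analysis does so. Likewise, having the fifth group among those compared is not an error in itself: the comparison is that group's stated purpose.

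**Conclusion.** The point holds as a mismatch between design and stated analysis. It does not show a wrong sample size or a large, certain loss of power. The arms form a complete 2x2; the protocol fixes one-way, pairwise and within-arm methods; and it names neither a combined anti-Hp effect nor an interaction.

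The size of the gain rests on the effect without iron, for which the protocol gives no figure. At its own 95% v 60%, the stratified test ranges from 93% down to 48% over the assumed rates shown, against 88% for the sized contrast. With a continuous outcome it is the better test only if the effect without iron exceeds about 41% of that with iron. The interaction can be estimated but is not powered: about 1.17 SD would be needed. What is gained for certain is a between-arm comparison of the changes and an estimate of the quantity on which the mechanism turns.

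**What to change.** In Data Analysis of the H. pylori protocol, replace the within-arm tests of outcome change, and any one-way ANOVA of outcomes, by one between-arm model on the four randomised arms with terms for anti-Hp, iron and their interaction. For correction of anaemia, use a Mantel-Haenszel analysis stratified by iron. Then state that:

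1. (ii) minus (iii), the contrast sized in 2.3, is the main comparison.
2. The anti-Hp effect stratified by iron, using all four arms, is reported beside it.
3. The interaction is reported with its confidence interval and its scale (for example, risk difference or odds ratio), and is estimated, not powered.
4. The non-randomised fifth group stays out of this model and is compared separately.

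The cost is analysis wording only: no more women, visits or measurements. The one downside is that the combined effect is an average and is diluted if anti-Hp works only together with iron, so it must not replace (ii) v (iii).
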